8.3.4.4 T cell receptor (TCR) deep sequencing

For each individual dose level, and for each dose-expansion cohort the change in tumor-infiltrating TCR between pre-treatment and post-cystectomy after treatment will be assessed by calculating the number of unique clonotypes comprising the top 25th percentile of cumulative reads after sorting by clone abundance. Repertoire change between sequencing experiments will be measured using Morisita's distance.

8.3.4.5 Genomic signatures of response

It is hypothesized that tumors with highly mutated or copy-aberrant genomes will either overexpress native proteins or express novel mutant proteins, both of which may be recognized by the immune system and serve as tumor-specific antigens. Therefore the effect of genomic mutations on the immune landscape will be investigated in each of the expansion cohorts in this study as follows.

Tumor DNA will be isolated from pre-treatment tissue and from post-cystectomy specimens, and will be analyzed for copy number using the Human Genome CGH 244K Microarray (Agilent, Santa Clara, CA) and/or by next-generation sequencing. Results will be analyzed with DNA Analytics software (Agilent) and with the assistance of the UCSF Genome Core and the UCSF Biostatistics core. For copy number paired Wilcoxon signed-rank test will be applied to test difference of tumor gene copy number between pre and post treatment. Two-sample Wilcoxon signed-rank test will be used to test the gene copy number between tumor responders and non-responders for pre-treatment, post-treatment and changes before and after the treatment, separately. Multiple testing adjustment will be done by controlling false positive rate. Next-generation sequencing will take place using appropriate methods and biostatistical analyses.

Annotation will be based on NCBI and UCSC databases. Chi-square test will be applied to obtain the significant variants associated with the clinical response.

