3.2 Number of Participants

Total Cohort A accrual: Up to 27 participants

- Cohort A Safety Lead-In: 18 participants (already accrued as of October 2020)
- Cohort A Expansion: Up to 9 additional participants may be accrued so that Cohort A expansion group = up to 15 total participants treated at established regimen (6 participants treated at highest administered dose from multi-dose portion + up to 9 additional participants).

Total Cohort B accrual: 21-33 patients

- Cohort B Safety Lead-In: 6-18 patients will be included.
- Cohort B Expansion: 15 additional patients treated with the regimen established during the safety lead-in phase (21 total treated with established regimen)

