8.1 Determination of Sample Size and Power Calculation

Cohort A

Multi-dose phase: With 6 patients in each cohort, there will be 80% of power to detect the effect size of 1.5 at significance level of 0.1. For the lowest dose level, a 2-fold increase from pre-treatment to post- treatment is expected, if at the higher dose level, there is more than 3-fold increase, assuming the standard deviation equals 1, then there will be 80% power to detect significant treatment effect on the intratumoral immune response.

Expansion phase: Data from a study of intravesical valrubicin chemotherapy in BCG refractory patients³⁴ demonstrated that a 21% CR rate is achievable at 6 months. Assuming a 5% (null) CR rate for untreated patients at 6 months, 15 patients would be required to observe an improvement to a 36% CR rate at 6 months in response to-PD-L1 therapy (effect size = 0.642), at a significance level of 0.1 with 80% power.

Cohort B

A pT0 rate at cystectomy was observed for ~30% of patients treated with immune checkpoint inhibitors monotherapy based on published Phase II clinical trials. In order to observe an improvement from a 30% CR rate (null hypothesis) to 60% CR rate (alternative hypothesis) with the combination of atezolizumab and tiragolumab a total of 21 patients are required in Cohort B assuming a significance level of 0.05 and 80% power.

Using these assumptions, following a lead in safety phase of 6 patients at a combination regimen that is deemed to be safe based on the criteria outlined above, a further 15 patients will be enrolled at the same regimen. This will make a total of 21 patients to be treated in Cohort B with the intended regimen.

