8.3.4.3 Immune cell mRNA signatures of response

To identify individual genes whose expression levels at pre-treatment are associated with pCR, we will apply two-sample *t* tests to compare responders and non-responders. Adjusted P values controlling for false discovery rate (Benjamini and Hochberg method) will be derived. In addition, to assess association of pre-specified immune gene signature with response, the median expression level of the component genes will be used to represent the signature and two-sample *t* tests will be used. For genes or signatures that emerge as significantly associated with response, logistic regression models will be used to assess their independent association with response after adjusting for known clinical prognostic factors. To identify pharmacodynamic markers, paired *t*-test will be carried out to examine immune gene expression differences between pre-treatment and at-cystectomy samples. Additionally, association of gene expression levels at time of cystectomy with long term efficacy outcomes, such as PFS and DFS, will be explored using the Cox proportional hazards regression model. Hierarchical clustering superimposed with response status, relevant baseline or prognostic characteristics or experimental factors will be performed using Spearman correlation and complete linkage to visualize the discriminating power of the immune gene expression and the correlative structure among the genes and the samples.

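### The exploratory genomic analysis (8.3.4.5) uses chi-square in very small cohorts, states no clear multiplicity control for variants, and names a paired test for independent groups

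*Combined protocol and SAP*

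**What the plan says.** Section 8.3.4.5 covers copy number and sequence variants. The effect of genomic mutations on the immune landscape "will be investigated in each of the expansion cohorts in this study as follows", so the cohorts are analysed separately. Section 3.2 gives the first size: "Cohort A expansion group = up to 15 total participants treated at established regimen". Section 8.1 gives the second: "This will make a total of 21 patients to be treated in Cohort B with the intended regimen".

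In order, the section specifies:
- Copy number, before against after treatment: "For copy number paired Wilcoxon signed-rank test will be applied to test difference of tumor gene copy number between pre and post treatment". This suits paired data.
- Copy number by response: "Two-sample Wilcoxon signed-rank test will be used to test the gene copy number between tumor responders and non-responders". It applies to the pre-treatment values, the post-treatment values and the change.
- Multiplicity: "Multiple testing adjustment will be done by controlling false positive rate".
- Sequencing, introduced after that sentence. For variants: "Chi-square test will be applied to obtain the significant variants associated with the clinical response".

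The plan chooses differently elsewhere. Section 8.3.3.2 uses Fisher's exact test for PD-L1/PD-1 against response in the same expansion cohorts. Sections 8.3.2 and 8.3.5.2 use the Wilcoxon rank-sum test for independent groups, the latter for responders against non-responders. Section 8.3.4.3 says of the mRNA genes: "Adjusted P values controlling for false discovery rate (Benjamini and Hochberg method) will be derived".

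**The concern.** Three stated methods do not fit the data they are meant for.

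1. The chi-square p-value is a large-sample approximation. In cohorts this small, split by response and by carrier status, it can be well off, and no exact or corrected version is named.
2. Read literally, a false positive rate is the level of each single test, which is not an adjustment for testing many genes. The sentence also precedes the variant test and belongs to the copy-number tests, so it is unclear whether variants are adjusted at all.
3. A signed-rank test needs pairs. Responders and non-responders are different patients, usually in unequal numbers.

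Section 2.3 lists mutations and copy-number aberrations associated with response and resistance among the exploratory endpoints. What is at stake is the credibility of that list: from the same data, two analysts following this section could report different significant findings.

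**Working it through.** **Inputs.** Cohort sizes: up to 15 (3.2) and 21 (8.1). Cohort B response: 30% null and 60% alternative (8.1), so 0.30×21 = 6.3, about 6 responders, or 0.60×21 = 12.6, about 13. Cohort A expansion target: 36% (8.1), so 0.36×15 = 5.4, about 5 responders. Section 8.3.4.5 gives no number of tests, significance level or carrier frequencies. Assumed: a nominal 5% level, 100 to 20,000 tests, and carrier frequencies of 5% to 50%.

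**The plan's own figure.** The 21 for Cohort B reproduces with the two-sided arcsine formula: h = 2·arcsin√0.6 − 2·arcsin√0.3 = 0.613, and n = (1.960+0.842)²/0.613² = 20.9, rounded up to 21.

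**Expected counts.** With n patients, R responders and m carriers, the smallest expected cell is min(R, n−R)·min(m, n−m)/n. Its largest possible value is 7×7/15 = 3.27 for 15 patients and 10×10/21 = 4.76 for 21. So no 2x2 table in either cohort has all expected counts at 5 or more. With 6 responders of 21, the smallest expected count is below 1 only for variants with up to three carriers (3×6/21 = 0.86; four carriers give 1.14).

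**One example.** 21 patients, 6 responders, two carriers who both respond:
- Pearson chi-square = 21×(2×15 − 0×4)²/(2×19×6×15) = 5.53, p = 0.019.
- Fisher: C(6,2)/C(21,2) = 15/210 = 0.071.

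**True size at nominal 5%, margins fixed.** Add the hypergeometric probabilities of all tables with chi-square p ≤ 0.05.
- 21 patients, 6 responders, 2 carriers: only the table above rejects, so 15/210 = 7.1%.
- 21 patients, 6 responders, 7 carriers: tables with 0, or with 4 or more, responding carriers reject. At 0 and at 4, chi-square = 21×42²/(7×14×6×15) = 4.2, p = 0.040. The size is (6,435 + 6,825 + 630 + 15)/116,280 = 12.0%.
- 15 patients, 5 responders, 2 carriers: C(5,2)/C(15,2) = 10/105 = 9.5%.

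The full run for 21 patients and 6 responders:

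| Carriers | 1 | 2 | 3 | 4 | 5 | 6 | 7 | 8 | 9 | 10 |
|---|---|---|---|---|---|---|---|---|---|---|
| Chi-square size, % | 0 | 7.1 | 1.5 | 5.3 | 1.1 | 3.1 | 12.0 | 4.6 | 4.6 | 6.3 |
| Fisher size, % | 0 | 0 | 1.5 | 0.3 | 1.1 | 3.1 | 0.6 | 4.6 | 4.6 | 1.2 |

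With 13 responders, two carriers give 0% and five give 11.1% for chi-square. Fisher's exact test never exceeds 5%.

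**Averaged over margins.** Chi-square size is 1.2% to 5.6% for 21 patients at 30% or 60% response. For 15 patients it is 1.6% to 4.5% at 36% response, and 3.6% to 5.3% at an assumed 20%.

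**Multiplicity.** Expected false hits without adjustment = 0.05 × number of null tests: 100 tests give 5, 500 give 25, and 20,000 give 1,000. Rare variants give fewer, because the actual size is then often below 5%.

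**Signed-rank.** No arithmetic applies. The statistic ranks within-pair differences, and no pairing exists between responders and non-responders.

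**The case against.** The strongest reply is that these are wording slips in an exploratory section, with little effect. Much of it stands.

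- A reader might infer that the chi-square test will generally produce spurious variants. The figures do not support that: averaged over margins its size is close to or below 5%, and the excess is confined to particular margins. What remains is that those margins can occur, that the analyst cannot choose them, and that an exact test is already in the plan.
- A reader might infer that expected counts fall below 1 throughout. That holds only for rare variants; below 5 holds for every table.
- Controlling a false positive rate may be a slip for false discovery rate, since the sentence announces an adjustment and 8.3.4.3 names Benjamini-Hochberg. This is plausible. Even so, no method or level is given, and coverage of the variant tests is not stated.
- A reader might multiply 5% by the 244K array and expect 12,200 false calls. The documents do not support this. It needs the literal reading of the sentence and one test per probe, whereas the section tests gene copy number and allows sequencing with or instead of the array.
- The signed-rank wording is probably a misnomer for rank-sum: the text calls it two-sample, and other sections name the right test. It concerns copy number, so it cannot create false variants. It is still the only specification for three comparisons, and it cannot be carried out as written.

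**Conclusion.** The point holds as three corrections to one exploratory section.

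- **Chi-square.** It is the wrong default at these sizes. Its true size can reach 7.1% or 12.0% (21 patients, 6 responders, 2 or 7 carriers) or 9.5% (15 patients, 5 responders, 2 carriers), although it is near or below 5% at many other margins. These figures assume the uncorrected statistic and a nominal 5% level.
- **Multiplicity.** This is the gap with the larger potential effect. As the section stands, the variant tests have no stated adjustment. The 5 to 1,000 false hits rest on an assumed 100 to 20,000 null tests at 5%; the plan gives no number.
- **Signed-rank.** The test named for copy number by response does not apply to independent groups.

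No primary or secondary conclusion, sample size or stopping rule depends on this section. Severity is low.

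**What to change.** In 8.3.4.5:
- Replace the chi-square test for variants with Fisher's exact test, as in 8.3.3.2.
- Replace the signed-rank test for responders against non-responders with the Wilcoxon rank-sum test, as in 8.3.2 and 8.3.5.2. Keep the paired signed-rank test for before against after treatment.
- Replace the multiplicity sentence with Benjamini-Hochberg control of the false discovery rate, as in 8.3.4.3. State the level, and say that it covers both copy number and variants.

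It would also help to set a minimum number of carriers for a variant to be tested, and to label the results as hypothesis-generating.

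The change needs no new patients or data. The cost is fewer declared variants, and in Cohort A possibly none. With 15 patients and 5 responders, the smallest attainable Fisher p-value is 1/C(15,5) = 1/3,003 = 0.00033. A lone hit among 500 tests would need 0.05/500 = 0.0001. That limit comes from the cohort size, and the report should say so.

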8.3.5 Analysis of Exploratory Endpoints: Immune endpoints

8.3.5.1 Immune cell activation

For each cohort individually, and for each individual expansion cohort, flow cytometry of circulating immune cell subsets will also be performed on pre-treatment blood and again after cystectomy. Established flow cytometry panels will examine T cell activation. Immune cell quantification will be summarized by changes from baseline to after treatment using descriptive statistics. Furthermore, paired Wilcoxon signed-rank test will be applied to test the pre-post treatment changes. When available, immune cells digested from resected tumor tissues will also be assessed by flow cytometry.

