2.3 Exploratory (Correlative) Objectives

1. To define the immunologic infiltration within bladder tissue following administration of neoadjuvant combination treatment with atezolizumab and tiragolumab when compared to pre-treatment TURBT biopsies
2. To assess the immunologic impact of combined tiragolumab and atezolizumab regimen in the urothelial cancer tumor microenvironment (Cohort B) in comparison to the impact on the tumor microenvironment of atezolizumab monotherapy in a similar cohort of patients treated with neoadjuvant atezolizumab for MIBC at UCSF (Cohort A)
3. To assess for tumor-based biomarkers of response and resistance to this combination therapy using single-cell RNA sequencing (scRNA-seq) and high-dimensional flow cytometry
4. To define the treatment-induced effects on circulating immune cells with this combination therapy
5. To assess the presence of antigen-specific immune responses to a broad panel of candidate tumor antigens

Endpoints:

- Immunohistochemistry and gene expression analysis for immune cell subset quantification and localization within resected tumors, in particular through the comparison of intratumoral environment of post-treatment cystectomies to pre-treatment TURBTs
- Flow cytometry to evaluate changes in intratumoral and circulating immune cells
- T cell receptor (TCR) deep sequencing of tissue samples from pre-treatment biopsies and post-treatment resected tissues, and post-cystectomy circulating T cells.
- Immune response mRNA expression analysis to derive signatures associated with tumor response
- Identification of genomic mutations and gene copy aberrations associated with response and resistance to therapy
- Antigen array-base detection of circulating antibody responses
- Flow cytometry to evaluate changes in intratumoral and circulating immune cells
- T cell receptor (TCR) deep sequencing of tissue samples from pre-treatment biopsies and post-treatment resected tissues, and post-cystectomy circulating T cells.
- Immune response mRNA expression analysis to derive signatures associated with tumor response (expansion only)

- Identification of genomic mutations and gene copy aberrations associated with response and resistance to therapy (expansion only)
- Antigen array-base detection of circulating antibody responses (expansion only)

3 Study Design

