6.9.3 End of Treatment (prior to cystectomy)

To be completed within 30 days of the last dose of study drug and prior to cystectomy.

- Physical examination
- Vital signs
- Performance Status
- Evaluation of adverse events
- Concomitant medications
- Local Laboratory Assessments. Unless otherwise noted, they may be obtained up to 96 hours prior to the visit:
 - Hematology assessment, including CBC with differential and platelet count
 - Blood chemistry assessment, including: glucose, BUN, creatinine, sodium, potassium, magnesium, chloride, bicarbonate, calcium, phosphorus, total bilirubin, ALT, AST, alkaline phosphatase, LDH, total protein, and albumin
 - C-reactive protein
 - Urinalysis
 - TSH, T3 and T4
- Central laboratory assessments
 - Immunologic and pharmacodynamic evaluations
 - TBNK blood sample
 - Plasma, serum, and blood sample for PD biomarkers
 - Urine sample for cytokine assessment.
- Imaging (CT or MRI) of the abdomen, and pelvis for tumor/lesion assessment, and if clinically indicated, imaging of the chest (CXR or CT).

Imaging of the upper tracts with an intravenous pyelogram, CT urography, renal ultrasound with retrograde pyelogram, ureteroscopy, or MRI urogram should be performed if clinically indicated.

- No repeat TURBT is required after the initiation of study therapy, however if performed per institutional standard of care then any tissue or other tumor biopsy should be obtained for analysis.

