8.3.5.2 Circulating antibody detection and characterization

Spotted antigen arrays will be used to detect circulating antibodies will be performed on sera derived from the pretreatment and post-cystectomy timepoints. After standard preprocessing of the protein array data, Cluster and Treeview software will be used for unsupervised clustering of the data with Pearson correlation and complete linkage. For each array, an antigen is identified as being detected if its value is above the median. To determine the number of up- and downmodulated antibodies, the difference in log₂ intensity values of pretreatment and post-treatment samples will be taken for each patient to identify antigens that are detected differentially due to treatment. Number of antibodies with at least 2- or 4-fold difference between pretreatment and post-treatment samples will be compared between clinical responders and nonresponders by performing two-sided Wilcoxon rank sum test.

9 Study Management

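### The circulating immune-cell and antibody contrasts run from before treatment to after cystectomy, so they cannot separate the drug effect from surgery; a scheduled pre-surgery sample could serve instead

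*Combined protocol and SAP*

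**What the plan says.** The fourth exploratory objective in section 2.3 is about cause: "To define the treatment-induced effects on circulating immune cells with this combination therapy".

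Section 8.3.5.1 sets the blood time points: flow cytometry on circulating cells "will also be performed on pre-treatment blood and again after cystectomy". It then states that a "paired Wilcoxon signed-rank test will be applied to test the pre-post treatment changes".

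Section 8.3.5.2 has the antigen arrays "performed on sera derived from the pretreatment and post-cystectomy timepoints". Within-patient differences in log2 intensity are taken "to identify antigens that are detected differentially due to treatment". The only formal test there is a two-sided rank-sum test comparing responders with nonresponders on the number of antibodies showing a 2-fold or 4-fold difference.

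Neither section mentions surgery as a source of change, and neither says which post-cystectomy visit supplies the sample.

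The protocol also schedules blood after treatment and before surgery. The End of Treatment visit in 6.9.3 is "To be completed within 30 days of the last dose of study drug and prior to cystectomy". It includes a TBNK sample and plasma, serum and blood for pharmacodynamic markers. The study calendar (6.10) and Appendix 4 agree, and both also list samples on Day 1 of every cycle.

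**The concern.** Radical cystectomy with pelvic node dissection lies between the two blood draws. The tumour is removed, and the patient has had a major operation and is recovering from it. Every patient is planned for that operation and there is no untreated surgical group, so drug and surgery coincide completely in the within-patient change. No adjustment at the analysis stage can pull them apart.

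Surgery is not the only addition. Section 6.9.4 keeps patients in follow-up if they start a new anti-cancer therapy without progression. Section 5.1 records that, before Amendment 4.3, Cohort A patients with adverse pathology could elect adjuvant atezolizumab. A post-cystectomy sample drawn after either would carry that exposure too.

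At stake is the interpretation of two exploratory analyses. A change in circulating cells or antibodies could be reported as a drug effect when the data cannot show that it is one.

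**Working it through.** The documents give no sample size, power or effect size for these endpoints, so there is no figure to reproduce. The check sets the analysis time points against the sampling schedule and adds two short calculations.

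**Schedule against analysis.**

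| Draw | Scheduled in | Before surgery? | Named in 8.3.5.1 or 8.3.5.2? |
|---|---|---|---|
| Pre-treatment | 6.9.1, 6.9.2, Appendix 4 | Yes | Yes |
| Day 1 of later cycles | 6.9.2, Appendix 4 | Yes | No |
| End of Treatment | 6.9.3, 6.10, Appendix 4 | Yes | No |
| At time of cystectomy | Appendix 4 | Not stated | Unclear |
| Post-cystectomy visits | 6.9.4, 6.10, Appendix 4 | No | Yes, visit not specified |

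Section 6.6.2 says that blood is processed to cells, plasma and serum, so the End of Treatment draw yields the type of material that both assays need.

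**Timing relative to exposure.** Inputs: three doses on schedule at weeks 0, 3 and 6 (5.1); surgery no earlier than 3 weeks after the last dose (5.1.1), so week 9, and by week 12 (3.1); first post-operative visit at 4 weeks ± 1 week (6.9.4); tiragolumab half-life about 15 days (4.1.2). Take the fraction remaining, relative to just after the third dose, as 0.5^(days/15).

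- Earliest post-operative visit: 9 + 3 − 6 = 6 weeks after dose 3, or 42 days. 0.5^(42/15) = 0.144.
- Latest first post-operative visit: 12 + 5 − 6 = 11 weeks, or 77 days. 0.5^(77/15) = 0.028.
- End of Treatment at its 30-day limit: 0.5^(30/15) = 0.25.

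The post-operative sample is thus further from tiragolumab exposure (about 14% down to 3% remaining) than the End of Treatment sample (about 25% or more). This assumes single-exponential decline and three tiragolumab doses.

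**Illustration of the paired test.** Assumptions, none of them from the documents: zero drug effect; normally distributed paired changes with SD 1; a mean shift caused by surgery alone; two-sided alpha 0.05. The sample sizes are 6 (one lead-in dose level), 15 (Cohort B expansion) and 21 (Cohort B at the chosen regimen). There were 3,000 simulated trials per cell, so the simulation error is at most about √(0.25/3000) = 0.9 percentage points.

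| Assumed surgical shift (SD of paired change) | n=6 | n=15 | n=21 |
|---|---|---|---|
| 0 | 2.7% | 4.8% | 4.7% |
| 0.25 | 5% | 14% | 18% |
| 0.5 | 11% | 42% | 55% |
| 0.75 | 21% | 75% | 89% |
| 1.0 | 34% | 93% | 99% |

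Each entry is the proportion of trials in which the signed-rank test declares a change although the drug does nothing. The zero row represents a pre-surgery contrast under the same assumptions. At n=6 the test is conservative because the smallest attainable two-sided p-value is 2/2^6 = 0.031 and the next is 0.0625. The table applies to 8.3.5.1 only, since 8.3.5.2 has no paired test.

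**The case against.** Several points on the other side are fair.

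- **Tests differ.** A reader might infer that the planned tests in both sections are undermined. The documents do not support that. The rank-sum test in 8.3.5.2 compares two groups who are both planned for surgery, so a common surgical shift is largely shared. The Cohort A versus Cohort B comparison is in the same position. In 8.3.5.2 it is the attribution to treatment that is exposed. One reservation remains: adjuvant atezolizumab in Cohort A depended on pathologic stage, so a sample drawn after it began could differ between responders and nonresponders.
- **Pre-surgery samples.** A reader might infer that they will go unused. Section 6.6.2 says that on-treatment and discontinuation samples serve to measure biomarker change. What can be said is narrower: 8.3.5.1 and 8.3.5.2 name no contrast that uses them.
- **Wording.** Sections 8.3.4.4 and 8.3.4.5 use post-cystectomy loosely for tissue removed at surgery, and Appendix 4 lists a draw at cystectomy without saying whether it precedes incision. But 8.3.5.1 and 8.3.5.2 concern blood and sera, and 2.3 separately lists circulating T cells after cystectomy. Post-surgical blood appears to be intended.
- **Late samples have a purpose.** Section 8.2 argues that immune effects may take weeks to months and may act on recurrence after surgery. This stands as a reason to keep a late sample, not as a reason to make it the only post-treatment contrast.

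**Conclusion.** The point holds for the within-patient contrasts. The paired test in 8.3.5.1 and the treatment attribution in 8.3.5.2 cannot separate the drug effect from surgery, tumour removal or later anti-cancer therapy. This follows from the single-arm design and planned cystectomy for all, without any numerical assumption.

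Its size is unknown. A reader might infer that a significant change would be wholly surgical. The documents do not show this: they give no surgical effect size and nothing on whether one persists to the first post-operative visit. The simulated rates show only how the test would behave under assumed shifts.

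The primary and secondary endpoints, including pT0 rate and safety, are untouched, and no sample size or stopping decision depends on these analyses. This is a worthwhile, inexpensive improvement to exploratory analyses. Moving the time point removes surgery from the contrast; the result is still an uncontrolled before-and-after comparison.

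**What to change.** In 8.3.5.1 and 8.3.5.2:

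1. Name the End of Treatment, pre-cystectomy sample (6.9.3, Appendix 4) as the main post-treatment time point, paired with the pre-treatment sample.
2. Keep one specified post-cystectomy visit as a separate secondary contrast. Describe it as change after treatment and surgery, and do not attribute it to treatment.

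No new visit, patient or blood draw is needed. A reader might infer that the change is free, but it is not quite. Assaying both time points means extra flow cytometry and array runs. The protocol also does not describe storage of viable cells from this visit, so the team must confirm that End of Treatment cells are usable for flow cytometry, or run the flow panels fresh at that visit. Serum for the arrays is already collected there.
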